Daily screening for inclusion/exclusion criteria will be conducted by the research team for patients admitted to VCUMC Medical Respiratory ICU (MRICU) and CMH ICU via EHR bedboards (via Epic) for both sites. For VCU Medical Center patients meeting inclusion criteria, a member of the study team will approach the patient at the bedside to review the informed consent form and answer any questions the patient may have before signing the consent. If the patient is not alert and oriented (as determined by the most recent physical assessment in the EHR and verified by the study team member bedside when engaging with the patient), the patient's LAR will be approached for consent, either in person in the intensive care unit (in the patient's room or in the dedicated family conference room to provide for privacy), or by phone (via number for LAR in EHR) if not available in person. The informed consent form will be reviewed with the LAR and questions answered by a member of the study team before signing. If the LAR does not answer when called, a message will be left via voicemail indicating that their family member may be eligible for participation in a clinical research study. They will be asked to call the study team member back at their convenience. If the LAR does not call back that day, a member of the study team will reach back out the next day. Failure to return a second message before the end of that day will indicate the desire to not have their family member participate and the LAR will not be contacted any further. The same procedures will occur for patients at CMH that meet study criteria. However, all in-person interactions planned for the VCU Medical Center site will be transferred to electronic means via Zoom. The designated study team member at CMH will bring the study dedicated iPad to the patient's bedside to engage with patients and/or their LAR. If the LAR desires, there will also be a dedicated private room at CMH where LARs can engage with the study team member reviewing the consent via Zoom. Although LAR consent will be required for enrollment of patients that are not alert and/or oriented, patient assent will be sought whenever possible.

5. * Does this study have a separate protocol document (i.e. a multisite or sponsor's protocol) that contains a detailed description of the study's methodology?

- Yes
 No

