Physical risk: The addition of a weighted blanket increases the amount of pressure placed on a patient's skin. Additionally, the weight of the blanket itself increases the risk of injury for the nurse applying the blanket to the patient each night (related to lifting of blanket).

Research data risk: There is a risk of loss of confidentiality and privacy for data collected from the patient's EHR record.

2. * Describe how each of the risks/harms/discomforts identified above will be minimized:

The minimize the physical risk for patients, exclusion criteria have been designed to eliminate enrollment of those with skin breakdown, or risk thereof.

The design of the study includes no additional safeguards for the nurses moving the weighted blankets. However, the weight of the blankets does not exceed lifting requirements of unit nurses. Additionally, proper body mechanics are fundamental to nursing education received by all nurses.

To minimize the risk of loss of confidentiality and privacy, only study team members will have access to the data collected. Additionally, data collected will be stored in REDCap, a secure system endorsed by VCU. Only aggregated, de-identified data will be used for reporting purposes.

3. * Describe any potential risks or harms to a community or a specific population based on study findings (e.g. information that could be stigmatizing or derogatory):

Not applicable.

4. Where appropriate, discuss provisions for ensuring necessary medical, professional, or psychological intervention in the event of adverse events to the subjects:

Although unlikely, any skin injury as a result of weighted blanket use would be medically treated as all other developing skin injuries. Additionally, use of the weighted blanket would immediately cease.

5. * Describe criteria for when the investigator would withdraw an individual participant from the study; such as safety or toxicity concerns, emotional distress, inability to comply with the protocol, etc.:

The investigator would withdrawal an individual participant from the study if any skin changes are noted on daily physical examinations, the patient experiences increased agitation with blanket use as reported by the patient's nurse, or the patient displays a lack of assent over blanket use.

6. * Summarize any pre-specified criteria that would trigger the investigator/sponsor/monitoring committee to stop or change the study protocol due to safety concerns:

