ICU patients most at risk for development of delirium are crucial to answering the aims of this study. It is common for ICU patients to have limited decisional capacity during their ICU level of care due to their medical conditions and/or sedative medications they are receiving. Decisional impairment for ICU patients may be temporary (i.e., resolves when sedating medication is decreased or removed) or permanent (i.e., the mechanism of their medical conditions is permanent in nature).

3. * Describe methods for determining whether participants are capable of providing consent or assent.

The study team will determine consent capability by utilizing a primary method, followed by a secondary confirmation. To obtain primary determination, the study team will examine the patient's EHR documentation of neurological status. Per the EHR, is the patient alert and orientated? If yes, the study team member obtaining consent will proceed to the patient's bedside. During the informed consent discussion, the study team member will pay close attention to any actions and/or communication from the patient that is not in alignment with the patient's documented mental status. If there are ever any doubts, the LAR will be sought for primary consent with patient assent.

4. * If a participant is capable of exercising some judgment concerning the nature of the study, describe how assent will be obtained.

Three scenarios are possible. If the patient is awake and capable of signing, a signature of assent will be asked from the patient following LAR consent. If the patient is awake but not able to sign, the patient will be asked to give some sign of assent (i.e., head nod yes, thumbs up). However, there is a case where patient assent may not be possible, and therefore, the study team will need to solely rely on LAR consent only. This situation would be related to a patient that has a medical condition or sedation that prevents their alertness.

5. Describe, if applicable, how the individuals' ability to give consent will be assessed throughout the study and how consent will be obtained when appropriate.

Throughout the study, continual assent will be assessed by members of the study team. At any point the patient's assent does not seem clear, the patient will be withdrawn from the study.

6. * Describe how and when consent will be obtained from participants' legally authorized representative (LAR).

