8. * Select the processes for minimizing any potential perception of undue influence to participate, particularly when there is a pre-existing relationship between the participant and the researcher (e.g. treatment provider/patient; instructor/student; supervisor/employee, etc.):

- Having a 3rd person (family/friends, another study team member, etc.) present during the consent / assent discussion
- Having an independent advocate (e.g. advocate for decisionally impaired adults, wards) present during the consent / assent discussion
- Removing physical symbols of authority like white coats or police badges
- Sitting down beside the participant instead of standing over them
- If obtaining consent / assent in a clinical setting, letting patients sit instead of lie down (if they are able to)
- Moving to a more neutral location like a conference room
- Obtaining consent / assent after other services/interactions have been completed (e.g. after school or the clinic visit)
- Having a mandatory wait period for the participant to go home and think before they sign consent /assent
- Sharing the consent / assent discussion between two people (i.e. a clinician might be the best person to explain study procedures and risks, but then they could step out and let a research assistant finish the consent process)
- Other protection(s) not listed here describe below
- N/A: Requesting Waiver of Consent

9. * Describe the other ways the study team will minimize any potential perception of undue influence to participate:

The study team will emphasize that the trial is voluntary and standard of care will be performed with or without consenting.

10. * How much time will participants be given to make a decision:

The patient and/or their LAR will be given as much time as possible to make a decision, as long as it is within the indicated 72 hour time frame.

11. If applicable, describe the procedures for consenting children upon entering adulthood or participants who are no longer decisionally impaired:

Continual assent will be sought for any patient enrolled that is decisionally impaired. This will enable the team to ensure their assent if they become no longer decisionally impaired.

Consent Groups

1. * Enter a descriptive name for this consent / assent group:

Healthcare Provider

2. * Select all that apply to this consent / assent group:

Name

- Signed Consent by Participant

- Signed Parent/Guardian Permission or Legally Authorized Representative Consent

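### The rule withdrawing patients whose assent is unclear conflicts with enrolment on LAR consent alone and with the narrower criterion in the risk section, so withdrawal could depend on mental status

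*Combined protocol and SAP*

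**What the plan says.** All references are to the combined protocol and SAP.

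- **Decisionally Impaired Adults, question 2** says why these patients are included: "ICU patients most at risk for development of delirium are crucial to answering the aims of this study".
- **Question 3** of that section sends doubt about capacity at the consent discussion to the LAR, not to exclusion: "If there are ever any doubts, the LAR will be sought for primary consent with patient assent".
- **Question 4** gives three assent scenarios: a signature, a gesture, or no assent at all. In the third, "the study team will need to solely rely on LAR consent only", and the text adds: "This situation would be related to a patient that has a medical condition or sedation that prevents their alertness".
- **Question 5**, the next answer, has the team assess assent throughout the study and then states: "At any point the patient's assent does not seem clear, the patient will be withdrawn from the study".
- **Risks, Discomforts, Potential Harms and Monitoring, question 5**, which asks for the withdrawal criteria, names skin changes, increased agitation with the blanket, "or the patient displays a lack of assent over blanket use".
- **Study Procedures, question 6** gives three grounds for withdrawal: participant request, an adverse event, and a request by the clinical team. It does not mention assent.
- **Study Procedures, question 4** treats assent as conditional: "patient assent will be sought whenever possible".
- **Consent Groups (Patient Participant), question 11**: "Continual assent will be sought for any patient enrolled that is decisionally impaired".

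**The concern.** The plan admits patients who cannot show assent and, in the next answer, orders the withdrawal of anyone whose assent is unclear. It also has two different thresholds for withdrawing on assent. One is uncertainty about assent. The other is a visible sign that assent is lacking.

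This matters to the statistics because the Background section describes delirium as a disturbance of cognition, attention and awareness. Such a disturbance can itself make assent unclear. A withdrawal rule keyed to unclear assent can therefore be triggered by the condition that Aim 3 sets out to describe. Follow-up would then be cut short informatively.

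Acceptability under Aim 1 is affected too. A patient who rejects the blanket says something about the blanket. A patient too sedated or confused to respond does not. If both are counted as withdrawn for assent, the count cannot be interpreted.

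**Working it through.** The plan states no figure on this point and no formula applies, so the check sets the rules side by side for four kinds of patient.

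| Patient state | Decisionally Impaired Adults, Q4 | Decisionally Impaired Adults, Q5, read literally | Risks, Q5 | Study Procedures, Q6 |
|---|---|---|---|---|
| Not alert (illness or sedation) | Enrolled on LAR consent alone | Withdrawn: no clear assent can be seen | Not withdrawn for assent: nothing is displayed | Not listed |
| Awake, delirious, signs inconsistent | Gesture scenario | Withdrawn once assent is unclear | Not withdrawn for assent unless the behaviour counts as a displayed lack of it | Not listed |
| Awake, plainly objects | No assent given | Withdrawn | Withdrawn | Withdrawn if the objection counts as a participant request |
| Awake, plainly agrees | Signature or gesture | Stays | Stays | Stays |

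**Step 1: where the rules disagree.** In the last two rows the withdrawal rules agree, or can be read to agree. They part in the first two rows, where mental status prevents a clear sign. The conflict is therefore confined to patients whose mental state is impaired.

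**Step 2: whether the rule reaches these patients.** It does. Consent Groups, question 11 has assent sought continually from every enrolled patient who is decisionally impaired, so the question 5 test would be applied in this group.

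**Step 3: what withdrawal does to the data.** Under Study Procedures, question 6, enrolment ends at withdrawal or at transfer out of ICU-level care. The HIPAA section, question 2, describes the agitation and delirium scores, sedation and pain medication, ICU stay and ventilator days as collected during enrolment. Hourly rounding records blanket use. Withdrawal for unclear assent stops these series while the patient is impaired. Counts accumulated over the ICU stay, such as nights of blanket use or positive delirium assessments, can then only be equal to or lower than with full follow-up. A rate per observed day could move either way. Data already collected are not deleted. Surveys still follow withdrawal if the blanket was used for at least one night, but a patient withdrawn before that yields no survey.

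**Step 4: what can be separated afterwards.** The visible text has no distinction between assent not obtainable and objection expressed. The Data Collection Spreadsheet is listed among the uploaded documents but is not reproduced, so it may already hold such a distinction.

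**Step 5: size.** This would need the proportion of patients whose assent becomes unclear and the day on which it does. The documents give neither, so the effect cannot be calculated.

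**The case against.** The best defence is that question 5 was meant only for patients able to show assent. Assent is conditional elsewhere, and the consent section explains continual assent as a way to confirm agreement if patients regain capacity. The answer devoted to withdrawal criteria uses the narrower, displayed-lack wording. A reading under which question 5 empties question 4 would enrol patients only to withdraw them at once, which the authors can hardly have intended.

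This is plausible for the patient who is not alert, but the text does not say it. It also does not resolve the second row of the table. An awake delirious patient can give some sign, so question 5 applies on any reading, and it withdraws on a threshold that the risk section does not share.

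Four stronger readings are tempting but unsupported:

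- **A retention range.** Applying the Background section's delirium rates to the 50 patients gives 50 × 0.20 = 10 to 50 × 0.80 = 40 affected, and so retention as low as (50 − 40)/50 = 20%. This merges two populations: 60–80% is cited for ventilated patients and 20–50% for lower-acuity patients. The extreme needs every participant to be ventilated, which is not an inclusion criterion. It also needs the top rate to apply and every delirious patient to be withdrawn for unclear assent. The visible text does not name retention as a feasibility measure either.
- **Loss of all delirium-prone patients.** Patients at risk who are alert can consent, sign or nod. Sedated and delirious patients are also different cases: the LAR-only scenario covers only those who are not alert.
- **A biased comparison of the two hospitals.** Study Procedures, question 4 applies the same recruitment and consent procedures at both, with Zoom replacing in-person contact at Community Memorial Hospital. Nothing indicates that the assent rule would be applied differently by site.
- **Loss of the patient's whole record.** No passage says that data collected before withdrawal are discarded.

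**Conclusion.** The contradiction stands as written. Question 5 withdraws on unclear assent without exception, question 4 enrols patients who cannot assent, the risk section withdraws on a narrower sign, and Study Procedures lists neither. Taken literally, question 5 makes withdrawal depend on mental status. That would truncate the delirium, agitation and blanket-use data selectively, and it would blur inability to assent with rejection of the blanket.

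This conclusion rests on the literal wording and on the premise that delirium can make assent unclear, which follows from the protocol's own description of delirium. How many patients would be affected is unknown. If teams in practice withdrew only patients who objected, the selective truncation described here would not have arisen from this rule, but the report would need to say so.

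The Review Setup section records a continuing-review category limited to data analysis. Conduct may therefore no longer be changeable, and the remaining scope may be in reporting and in the planned larger trial.

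**What to change.** 1. Reconcile the assent and withdrawal statements in Study Procedures (questions 4 and 6), Risks (question 5), Decisionally Impaired Adults (questions 3 to 5) and Consent Groups (question 11) into one withdrawal rule used at both sites. Which rule applies is for the investigator and the IRB to decide.
2. Record *objection expressed* separately from *assent not obtainable*, if the data collection form does not already do so.
3. Report withdrawals by reason, by delirium status at the time, and by site. Count only expressed objections as evidence on acceptability.
4. If enrolment is over, state which rule was applied and produce the same table as far as records allow. Carry the reconciled wording into the larger trial.

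The cost is a wording change, at most two reason codes, and one small table. No extra patients are needed.

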 - equity or business ownership in a company that has yet to make a profit and is related to this project
 - conflict of time/effort,
 - personal and professional relationships/affiliations,
 - intellectual passions or personal beliefs
 - other factors that could create bias in the study
- Yes No
3. Describe any institutional conflict of interest that you or any member of the research team are aware of that pertains to this research:
- An institutional conflict of interest is a situation in which financial interests of the University or University leadership may affect research activities at VCU.

ID: MS12_HM20027241

View: SF2 - Other VCU Requirementsv2

Other VCU Requirements

This page asks questions on behalf of other ancillary offices, committees and departments at VCU regarding institutional requirements that could apply to this research. In some cases, these requirements could also impact the consent process or other aspects of the IRB's review.

Based upon answers provided earlier in this form, certain ancillary sections below may not have questions displayed if those requirements are not applicable to this study.

1. Cost Coverage Analysis

1. * VCU requires that all clinical research studies be evaluated to determine if a Coverage Analysis is required. Has your study been evaluated by an institutionally designated Coverage Analysis Specialist?

Yes
 No
 Not Applicable

2. ClinicalTrials.gov Program & OnCore

For guidance, see <https://ctr.vcu.edu/support/consultation/clinical-trials-gov/> or email [contact]

1. * Is this a Clinical Trial?

Yes No

2. * The PI acknowledges awareness of the following requirements for posting clinical trial consent forms:

- Each clinical trial under the 2018 Common Rule that is conducted or supported by a Federal department or agency must post one IRB-approved consent form that was used to enroll subjects on a publicly available Federal website [45 CFR 46.116(h)].

- When engaged in multi-site research, the VCU PI is responsible for confirming with the lead site who is responsible for posting the informed consent form.

- When VCU is the lead site, the VCU PI is responsible for posting the informed consent form (unless the federal department or agency will post it).

Yes No

3. Community Engagement

For more information, see <https://community.vcu.edu/>

1. * Is this a community engaged research study? (See help text for definitions)

Yes
 No

4. Family Educational Rights and Privacy Act (FERPA) Requirements

For guidance, see <https://rar.vcu.edu/records/family-educational-rights-and-privacy-act/>

1. * Does this study involve obtaining information from VCU students' educational records (see help text)?

Yes
 No

5. Research Data Privacy Requirements

Contact the VCU Research Data Privacy Office with questions: <https://research.vcu.edu/integrity-and-compliance/compliance/research-data-privacy/>

1. * Does this study involve the VCU site (regardless of the IRB of record), or any sites under the VCU IRB's oversight, obtaining data in, or from, a foreign country?

Yes No

6. Information Security

For guidance, see <https://ts.vcu.edu/askit/essential-computing/information-security/>

1. * Using the VCU Data Classification Tool, please determine the appropriate data classification category for the data that will be collected or used in this research.

Note: if the data falls into Category 1, a data security management plan is required by University Information Security Office.

See help text for information on accessing the VCU Data Classification Tool, and for information on creating a data security management plan at <https://dms.vcu.edu>.

Category 1: all data that require breach notifications in the event of improper release, including personally identifiable information covered by HIPAA and Commonwealth of Virginia regulations.

Category 2: all proprietary data that if improperly released has the potential to cause harm to the institution, its mission or its reputation that do not require breach notifications.

2. * I confirm use of the VCU Data Classification Tool at <https://go.vcu.edu/dataclassification> in determining the data classification category selected in Question 1:

Yes
 No

3. * The PI is aware that if the study's data is classified as Category 1, a Data Management Plan must be submitted to and approved by VCU Information Security prior to IRB approval. See <https://ts.vcu.edu/askit/essential-computing/information-security/data-management-system/>

Yes No

4. * I confirm that any use of external technology has been submitted to Information Security in the study's Data Management Plan. If this study uses any technology platforms, apps, services, etc. that are maintained external to VCU or hosted by another institution and are NOT currently listed in the DMS system as an approved service for the storage, processing, or transmission of VCU data, I am required

to have VCU Information Security conduct a security review of that technology. I may contact [contact] with questions.

I also confirm that if the study involves use of external technology and VCUHS HIPAA data, I must also seek security review from the VCUHS Data Governance group (contact [name] at [contact]):

- Yes
 No
 N/A - not using external technology

7. Massey Cancer Center Protocol Review and Monitoring Committee (PRMC)

For guidance, see https://www.masseycancercenter.org/research/~//link.aspx?_id=ee49e95faa8b44d09b6e89d8e3b48b57&_z=z

1. * Does this study involve any of the following?

- Research involving patients with cancer, their families or their health care providers
- Research involving cancer screening, diagnosis or prevention
- Secondary data collected from cancer patients or their medical records
- Cancer-related surveys (e.g., attitudes about risk, prevention and treatment) of the general population

- Yes
 No

8. VCU ONETRAC Protocol Review Oversight Committees (PROCs) For guidance, see <https://onetrac.vcu.edu/>

1. * Does this study involve research with any of the following?

- VCU Health System patients
- VCU Health System facilities
- VCU Health System data Yes

No

If Yes, upload documentation of approval or review by the PROC or PRMC in this studys topic area. If you do not have PROC or PRMC approval, please visit onetrac.vcu.edu for additional information and to submit your project for review.

9. VCU Health Department of Patient Centered Services

1. * Does your study involve a satisfaction survey administered to VCUHS patients (*See Help Text):

- Yes
 No
 Not Applicable

2. * Will research participants be offered any form of incentive or payment for study participation (*See Help Text):

- Yes
 No

10. VCU Faculty-Held IND or IDE

For guidance, see <https://research.vcu.edu/human-research/regulatory-affairs/>.

Questions related to if you need an IND or IDE for your study should be emailed to: [contact]. Please submit a copy of your FDA submission prior to submitting to the FDA to <https://redcap.vcu.edu/surveys/?s=NR7K7LR4JW>.

11. VCU Health System locations

1. * Will research activities occur in patient care areas of the VCU Health System (including at CHoR, Community Memorial Hospital, Tappahannock Hospital, VCU Medical Center and Massey Cancer Center)?

- Yes
 No

2. * The PI has reviewed and agreed to comply with the VCU Health System Research in Patient Care Areas policy (https://research.vcu.edu/compliance_program/vcuhs_policies.htm):

- Yes
 No

12. VCUHS Department of Pathology

Learn more about requesting and establishing an account with Pathology here: See <https://pathology.vcu.edu/research-services/>

1. * I have contacted VCUHS Department of Pathology to determine feasibility if my study involves the following:

- Storage of Microbiology isolates
- New instrumentation provided by clinical trial/study sponsor, or
- Non-routine specimen processing (examples include but arent limited to the following: addition of reagents to samples/aliquots, buffy coat processing, DNA sample processing)

- Yes
 No

N/A - my study does not involve any of the listed processes.

2. * If my study involves specimen retrieval from the Pathology laboratory, I have established a process with Pathology to deidentify and retrieve specimens.

Yes

No

N/A - my study won't involve specimen retrieval from Pathology

13. VCU Institutional Biosafety Committee (IBC)

To contact the Biosafety Office see their website at: <https://research.vcu.edu/integrity-and-compliance/compliance/regulatory-committees/>

1. * Does this project involve any of the following hazardous biological agents (biohazardous agents) that have NOT been FDA approved? These may include, but are not limited to, any of the following. If you are unsure, please contact the Biosafety Office:

- Any functional recombinant viruses (especially viruses that may integrate into the patients genome).

- Expression or administration of biological toxins.

- Live pathogenic or potentially pathogenic organisms of plants or animals (bacteria, fungi, wild-type viruses, parasites, etc.), that are, or potentially may be, in experimental products.

- Introduction or expression of rDNA or synthetic nucleic acids

- Use of a product (e.g., monoclonal antibodies, recombinant cytokines) produced from virally infected mammalian cells.

- Use of a product (purified growth factors, cytokines) produced from mammals or their cells.

Yes No

14. VCU Radiation Safety Committee (RSC)

To contact the Radiation Safety Section see their website at: <https://research.vcu.edu/integrity-and-compliance/compliance/regulatory-committees/>

1. * Does this study involve radiation exposure and/or scans involving radiation (e.g.: PET, MRA, CT, DXA, nuclear medicine, etc.)?

Yes

No

15. VCU Scientific Review Committee (SRC)

For guidance, see <https://ctr.vcu.edu/support/consultation/scientific-review-committee/>

1. * Has this human subjects protocol (not the grant application) already been reviewed by the funder of a sponsored project (e.g. a federal, state or non-profit funding sponsor)?

Yes

No

16. Upload any documents requested in the questions above:

ID: MS12_HM20027241

View: SF2 - HIPAA

HIPAA

In order for VCUHS to meet HIPAA regulations regarding accounting of disclosures, data retention, and data destruction requirements for PHI data obtained without patient authorization, members of the study team (including principal investigators) are directed to consult with VCU Informatics to obtain any VCUHS data. This does not include obtaining data for which the study team has patient authorization. [VCU Health System Authority and Affiliates Policy COMP-014]

For data requests, including preparatory to research and research with decedents, submit a request for the desired PHI, or for a consultation on alternate methods to obtain the data, at <https://informatics.vcu.edu>.

HIPAA Privacy Board Requirements

For guidance, see <https://www.vcuhealth.org/our-story/who-we-are/compliance-services/compliance-services>

1. * Select the source of the Individually Identifiable Health Information. See help text for definitions.

PHI associated with or derived from (i.e. obtained from or entered into) VCU Health medical records or VCU Dental Care records

Research Health Information (RHI) created or received by a study and kept solely in study records (e.g. self reported or the result of research tests and not entered into health records)

PHI associated with or derived from (i.e. obtained from or entered into) a non-VCU HIPAA covered entity's health records

2. * Summarize the types of health information that will be obtained or used in this research. Do not describe only the identifiers that you will collect or use during the study.

The following demographic information will be obtained from the participant's medical record while enrolled in the

study: Participant name, age, weight/BMI, sex, race and ethnicity, medial history/diagnoses, admission diagnoses, home zip code, admitting hospital (CMH or VCUMC)

The following health information will be collected from the participant's medical record while enrolled in the study: Participant medical history/diagnoses, admission diagnoses, agitation and delirium scores, sedation and pain medications given and amounts given, hospital length of stay, ICU length of stay, and number of days ventilated.

3. * Describe the source(s) of the protected health information (e.g. Informatics or which clinical databases):
The source of the PHI will be demographic and clinical data entered into the participant's EHR (Epic)
4. * Does the PI certify that this study's access to and use of the protected health information is limited to the minimum amount necessary to be able to effectively conduct the research?
 Yes No
5. * Select all pathways this research will employ to use or access PHI (selections will branch):
- De-Identified Data (none of the 18 identifiers are recorded or associated with the research data)
 - Limited Data Set
 - Waiver of Authorization
 - Partial Waiver of Authorization (temporary waiver for recruitment purposes and/or waiver of some elements of Authorization)
 - Signed Authorization Combined with Consent Form
 - Signed Authorization as Stand-Alone Form

ID: MS12_HM20027241

View: SF2 - Partial Waiver of Authorization

Partial Waiver of Authorization

1. * Select the purpose for requesting the partial waiver of authorization:
- Identify possible participants to recruit for the study
 - Waive some elements of authorization (such as signature)
2. * Explain how the partial waiver of authorization poses no greater than minimal risk to participants' privacy:
(Alternative question phrasing: How do the risk(s) of this use of identifiable health information compare to the risks to privacy a person might reasonably experience in normal everyday life?)
The request for partial waiver of authorization for the sole purpose of identifying possible participants to recruit for the study will be limited to patient participant inclusion/exclusion criteria. Thus, we will access the minimum amount of information needed to recruit potential participants. This access will be temporary and followed by full, signed authorization upon enrollment into the study, thereby obtaining full authorization for further use of the PHI for research analysis. If a potential participant chooses not to enroll in the study, no information about that potential participant will be retained or stored once study accrual objectives are met thereby posing no greater than minimal risk to privacy.
3. * If you selected "Identify possible participants to recruit" above, describe when will the 18 HIPAA identifiers be destroyed for those who do not eventually enroll in the study?
- Following Participant Contact
 - Upon Reaching Study Accrual Objectives
 - Other
4. * Other than the PI and research personnel identified in this research application, who else will have access to the Protected Health Information?
No one. Only as required by law.
5. * Explain why the study cannot practicably be conducted without the partial waiver of authorization:
(Alternative question phrasing: Why is this partial waiver necessary to make the study achievable or viable?)
We cannot identify individuals who meet inclusion and exclusion criteria without the partial waiver of consent (access to the PHI for screening purposes).
6. * In applying for a partial waiver of authorization, the PI agrees to the following:
- A) The identifiers used for this research study will not be used for any other purpose or disclosed to any other person or entity (aside from members of the research team identified in this application), except as required by law.
 - B) If at any time I want to reuse this information for other purposes or disclose the information to other individuals, I will seek approval from the IRB/Privacy Board.
 - C) I will comply with VCU HIPAA policies and procedures and to the use and disclosure restrictions described above.
 - D) I assume responsibility for all uses and disclosures of the PHI by members of my study team.
 Yes
 No

ID: MS12_HM20027241

View: SF2 - Institutional Requirements Complete

Institutional Requirements Complete

- Protocol Progress:
- ? INITIAL SETUP
- ? BACKGROUND, RATIONALE & GOALS
- ? RESEARCH PLAN
- ? CONSENT PLAN
- ? RISKS, PRIVACY & CONFIDENTIALITY
- ? POPULATIONS WITH SPECIAL CONSIDERATIONS
- ? INSTITUTIONAL REQUIREMENTS
- ? DOCUMENTS

Click Continue below to go to the next section

ID: MS12_HM20027241

View: SF2 - Documents

Documents

1. Upload any documents that the VCU IRB will need to conduct a review of this submission:

A list of potential documents is given in the help text.

NOTE: The delete function should only be used if an incorrect document is uploaded or added to the system AND that document has not been reviewed and approved by the IRB. Do NOT delete documents that the IRB previously reviewed and approved.

Once you have uploaded a document to RAMS-IRB, any changes to that document (i.e. different versions of the same document) should be added to the IRB submission by using the Update button. To provide updated documents, follow these steps:

- Click the Update button located to the left of the document to be updated.
- In the Add Document window, click the Choose File or Browse button, select the file you are adding, and click on the Open button.
- Click OK to close the Add Document window, and the system will upload the revised document. RAMS-IRB will automatically provide a version number for the document.

To access previous versions of a document in RAMS-IRB you must use the History link associated with the document.

- Click the View or Update button located to the left of the document you wish to access.
 - In the Add/View Document window, click the "History" hyperlink located to the right of the file name.
 - A separate window will open that shows all versions of the document that have been added to RAMS-IRB.
- Click on any file name to download and view the document.

	Document Name	Document	Version	Date Modified	Uploaded By	Type	Approved
View	Version 3_Weight Blanket Study Consent Form_5-23-2024_Clean.docx	Version 3_Weight Blanket Study Consent Form_5-23-2024_Clean.pdf	0.03	6/7/2024 1:56 PM	[name]	Consent/Assent/Information Sheet	Yes
View	Version 3_Weight Blanket Study Consent Form_5-22-2024_Redlined.docx	Version 3_Weight Blanket Study Consent Form_5-22-2024_Redlined.docx	0.01	5/22/2024 3:53 PM	[name]	Consent/Assent/Information Sheet	Yes
View	Consent Form	Weight Blanket Study Consent Form_10-11-2023 - Copy - Copy.pdf	0.04	10/11/2023 11:35 AM	[name]	Consent/Assent/Information Sheet	Yes
View	Weighted Blanket Device Information	Weighted Blanket Info for IRB_07 27 2023.docx	0.02	7/27/2023 10:29 AM	[name]	Other	Yes
